4.4 Per-protocol (PP) analysis set

The per-protocol (PP) analysis set will include all subjects in the mITT population who completed at least one eligible attack in compliance with the protocol and have no major protocol deviations. Subjects in the PP population will be analyzed as-treated.

Major protocol deviations defined as deviations which may impact subject safety, alter the risk/benefit ratio, compromise the integrity of the study primary end point data include, but are not limited to:

- Study treatment deviation for first eligible attack, e.g. baseline diary reported after treatment initiation, diary reported after treatment start, Baseline diary reported more than 30 minutes prior to the initiation of

treatment.

- PRO report outside of window for first eligible attack.

4.5

Statistical Analysis of Analysis Sets

As discussed in the introduction section to the SAP, a technical issue may have rendered the study device ineffective for those subjects treated prior to May 31, 2019. Since the treatments may not have been therapeutic, including them in the primary safety analysis may lead to under reporting of safety events. Consequently, the ITT data analysis set will serve as the principal data analysis set for the safety analyses. The safety analyses will also be performed on the Full Analysis set.

The mITT data analysis set will serve as the principal data analysis set for the efficacy analyses.

The primary and secondary efficacy assessments will also be performed on the per protocol (PP) and the ITT analysis sets.

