4.1 Full Analysis (FA) set

The Full Analysis (FA) set will include all the subjects randomized, including the subjects treated with the device up to May 31, 2019.

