4.2 Intent-to-Treat (ITT) analysis set

The Intent to Treat (ITT) analysis set will include all randomized subjects who were treated with the device after May 31, 2019 (including self-practice). Per ITT principles, all subjects will be analyzed as randomized.

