4.3 Modified Intent-to-Treat (mITT) analysis set

The mITT analysis set will include all subjects from the ITT analysis set who treat at least one eligible attack (excluding the "self-practice test"). Subjects in the mITT analysis set will be analyzed as treated.

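### The principal safety analysis groups subjects as randomized, and no safety analysis by device actually received is specified

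*SAP*

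**What the plan says.** SAP 4.5 names the sets for each purpose. For safety, "the ITT data analysis set will serve as the principal data analysis set for the safety analyses". For efficacy, "The mITT data analysis set will serve as the principal data analysis set for the efficacy analyses", with the per-protocol and ITT sets as further efficacy analyses.

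The grouping rules are in the set definitions:

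- **ITT (SAP 4.2):** "Per ITT principles, all subjects will be analyzed as randomized". Membership requires device use after 31 May 2019, and self-practice counts.
- **mITT (SAP 4.3):** "Subjects in the mITT analysis set will be analyzed as treated".
- **Per-protocol (SAP 4.4):** "Subjects in the PP population will be analyzed as-treated".
- **Full Analysis (SAP 4.1):** "The Full Analysis (FA) set will include all the subjects randomized, including the subjects treated with the device up to May 31, 2019". This defines membership only. SAP 4.5 adds that "The safety analyses will also be performed on the Full Analysis set".

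Protocol 11.6 has the same arrangement: ITT, as randomized, is the main set for safety, and mITT and per-protocol are as treated. Protocol 11.7.5 makes the cumulative incidence of device-related adverse events the primary safety variable and compares adverse event rates between the groups with Fisher's exact test.

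**The concern.** Adverse events follow from the stimulation a person receives, so safety is conventionally tabulated by actual exposure. Efficacy is conventionally analyzed as randomized, to keep the protection of randomization. For its principal analyses, this plan does the reverse.

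The two modes differ greatly. Protocol 5.3 sets the active device at 80 Hz with a phase duration of 330–400 microseconds, and the sham at 0.33 Hz with 70–100 microseconds. If a subject randomized to sham used an active device, the stated rule would place any resulting events in the sham column. A subject randomized to active who used a sham device would dilute the active column.

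If active stimulation causes more events, both errors shrink the observed difference and make the device look safer than it is. That is the non-conservative direction for a study meant to support FDA clearance (Protocol 3.2).

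The rule also sits awkwardly with the SAP's own reasoning. Section 4.5 keeps possibly ineffective early treatments out of the principal safety set because they could lead to under-reporting of events. That is an argument about real exposure, and as-randomized grouping does not carry it through.

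**Working it through.** The plan states no figure on this point, so there is none to reproduce. The check has two parts.

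**1. Rules side by side**

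| Analysis | Set | Grouping stated |
|---|---|---|
| Safety, principal | ITT | As randomized (SAP 4.2) |
| Safety, additional | Full Analysis | None stated (SAP 4.1) |
| Efficacy, principal | mITT | As treated (SAP 4.3) |
| Efficacy, supportive | Per-protocol | As treated (SAP 4.4) |
| Efficacy, supportive | ITT | As randomized (SAP 4.2) |

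No row gives safety by device received. Protocol 11.6 does not supply one, and the SAP Introduction says the SAP prevails where the two differ.

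**2. Size of the effect if devices were swapped**

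Inputs:
- Subjects per arm, N = 65. This is an assumption: half of the approximately 130 subjects that the SAP Introduction gives as enrolled for efficacy analysis, under 1:1 allocation.
- True adverse event rates by device, p_A and p_S. These are assumed; the documents give none.
- Number of swapped pairs, m. This is hypothetical; the documents report no swap.

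Expected rates when grouped as randomized:
- Active = [(N − m) p_A + m p_S] / N
- Sham = [(N − m) p_S + m p_A] / N
- Difference = (p_A − p_S)(1 − 2m/N)

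For 20% versus 5% and one pair:
- Active = (64 × 0.20 + 0.05)/65 = 19.77%
- Sham = (64 × 0.05 + 0.20)/65 = 5.23%
- Difference = 14.54 points, against a true 15.0. The factor is 1 − 2/65 = 0.969.

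| Assumed rates | True difference | 1 pair | 3 pairs | 5 pairs |
|---|---|---|---|---|
| 10% vs 2% | 8.0 | 7.75 | 7.26 | 6.77 |
| 20% vs 5% | 15.0 | 14.54 | 13.62 | 12.69 |
| 30% vs 10% | 20.0 | 19.38 | 18.15 | 16.92 |

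(All differences are in percentage points.)

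If only one subject is affected, randomized to sham but given an active device, the expected shift at 20% versus 5% is 15/65 = 0.23 points, leaving 14.77.

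A larger figure applies to a particular event. If one observed adverse event is moved from the active column to the sham column, each arm changes by 1/65 = 1.5 points and the difference by 2/65 = 3.1 points. This is conditional on the misassigned subject actually having had an event.

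With m = 0 the factor is 1, and the as-randomized and as-treated results are the same.

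**The case against.** The strongest reply is that no consequence is shown. The bias needs at least one subject who used the other arm's device, and neither document mentions one. The protocol and SAP also agree with each other, so the objection rests on general practice and not on an internal contradiction. Both statements are correct, and they limit the point to a precaution.

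A reader might infer more than the documents support in three ways:

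- **That the plan foresees dispensing errors.** The as-treated wording for mITT and per-protocol has practical effect only if received and randomized device can differ, but nothing ties it to dispensing errors. Protocol 5.3 and 8.4 describe identical appearance and packaging as a blinding measure. This suggests a swap would be hard to notice, not that one was expected or occurred.
- **That all efficacy is as treated.** The supportive ITT efficacy analysis is as randomized.
- **That the device logs already show which mode was delivered.** Protocol 8.1.5 lists study code, serial number, session date and a timeline of pass, fail and device-failure events; 8.6 adds duration and intensity. None of these is stated to identify active or sham. A pass needs only 2 mA, and both modes can exceed that under Protocol 5.3.

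Other safety outputs give partial protection. Serious events are listed and discussed individually (Protocol 11.7.5), and serious events and device effects receive narratives and adjudication (Protocol 10.1.2). These steps review relatedness and seriousness; they do not move a subject to the correct arm in the tables.

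Finally, the SAP is abridged, so the missing rule for the Full Analysis set may reflect the abridgement and should carry little weight. The as-randomized rule for ITT is explicit and does not depend on it.

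**Conclusion.** The point holds as a minor one. Followed as written, the rule would count a subject's adverse events under the wrong arm whenever received and randomized device differ, and no stated safety analysis corrects this.

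The documents do not support a claim that the safety results are biased. The effect is nil if no device was swapped. If some were, each swapped pair removes about 3% of the expected difference at 65 per arm, or about 0.5 points at assumed rates of 20% versus 5%. A shift of about 3 points should be quoted only for the case where one actual event is moved from active to sham. All these sizes rest on the assumed arm size, event rates and swap counts. Sample size, power and the alpha level are unaffected.

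**What to change.** Add to SAP 4.5 that safety analyses on the ITT and Full Analysis sets include subjects with any device use, self-practice included, grouped by the device actually received. State the source: the serial number in the device logs, reconciled to the allocation list after unblinding. The documents do not say that this list carries serial numbers, so the sponsor should confirm that each serial number can be linked to its preset mode. List any subject whose received device differs from the randomized one.

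The cost is a short addition to the text and a small reconciliation step. Protocol 8.1.7 already has the logs for each treated episode downloaded at Visit 4. If the reconciliation finds no discrepancy, regrouping leaves the comparison unchanged and the report can say so.
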